6.7 Missing Data Handling

The missing data pertinent to the validated instruments Skindex-16, and TSQM-9 will be handled per instrument owner instructions / scoring manual. For all study variables and endpoints, no missing data imputation is planned.

6.8 Significant Protocol Deviations

A protocol deviation is defined as any intentional or unintentional failure to follow the requirements and procedures described in the study protocol. Deviations may have occurred at the subject level or at the site level, and could have been recorded by the site, or uncovered data review. Considering the real-world study design of PROAK, reflecting the routine clinical practices in the U.S and associated patient encounters and routine/standard of care data documentation, patients are expected to miss clinic visits or reschedule planned visits as life situations change. These will not be considered as protocol deviations.

Significant protocol deviations will be flagged, and these are defined as study-related issues that were likely to result in: significant impairment of the rights, welfare or safety of subjects; misconduct and/or fraud; and significant impairment of the integrity/validity of study results. Significant protocol deviations also include issues that were likely to impair monitoring and oversight of the study.

6.9 Sensitivity Analyses

Sensitivity analyses will explore the impact of missing data on the robustness of the results, if unusual number of missing data is observed in the study. If some Subject visits are conducted via remote visits instead of in-person visits, the nature of visit (remote vs. in-person) may be used to stratify the analysis of secondary endpoint involving IGA, if sample size permits.

7 DATA TABLES

All patients who received at least one dose of tirbanibulin during the study observation period and had at least some data pertaining to study primary endpoints (PROs) at Week 8 will be included in **Full Analysis Set (FAS)** to facilitate the planned descriptive analysis.

Correspondingly, patients who completed the study survey at Week 8 will be included in FAS, since patients answering Week 8 survey will have completed all relevant PRO related questions.

Safety data analyses will be conducted among the **Safety Population**, that correspond to the entire study cohort that took at least one dose of tirbanibulin. Correspondingly, all patients completing the baseline survey and took at least one dose of tirbanibulin, amounting to N=300 will be included in this analysis.

Section 7.1 Patient Demographics, Perceptions & PROs (FAS Population)

Table 1.1 Population	25
Table 1.2 Patient Demographic Characteristics	26
Table 1.3 Patient Self-Assessment: AK Treatment Motivators.....	28
Table 1.4 Patient Self-Assessment: Baseline Skin Texture.....	28
Table 1.5 Patient Reported Medication Compliance.....	29
Table 1.6 SKINDEX-16: Patient Response Summary.....	30
Table 1.7 SKINDEX-16: CFB at Week-8 for Individual Items.....	36
Table 1.8 SKINDEX-16: Domain Scores.....	41
Table 1.9 Subgroup Analysis of SKINDEX-16 Domain Scores.....	42
Table 1.10 Patient Evaluation of Overall Appearance in the Original Treated Area.....	43
Table 1.11 Subgroup Analysis of Patient Evaluation of Overall Appearance in the Original Treated Area	44
Table 1.12 Treatment Satisfaction Questionnaire for Medication (TSQM-9): Patient Scores in the Original Treated Area.....	46
Table 1.13 Subgroup Analysis of TSQM-9 Patient Domain Scores	47
Table 1.14 Patient Satisfaction with Tirbanibulin in the Original Treated Area (looks/texture)	48
Table 1.15 Subgroup Analysis of Patient Satisfaction with Treatment Ability to Improve How Skin Looks in the Original Treated Area	49
Table 1.16 Subgroup Analysis of Patient Satisfaction with Treatment Ability to Improve Skin Texture in the Original Treated Area ..	51
Table 1.17 Patient Relative Satisfaction of Tirbanibulin in Comparison with Other Topical Medications for AK in the Original Treated Area	53
Table 1.18 Subgroup Analysis of Patient Relative Satisfaction of Tirbanibulin, Regarding Duration of Skin Reactions	56
Table 1.19 Subgroup Analysis of Patient Relative Satisfaction of Tirbanibulin, Regarding Severity of Skin Reactions	58

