7.3 Second Study Encounter

At the completion of 8 weeks (\pm 7 days) post-index date, the Site Investigators and Subjects will be asked to complete the data collection corresponding to the study primary endpoints. The subject encounters (post-baseline) are expected to take place during in-person subject visits to the clinic, but remote/virtual visits may be allowed where COVID-related protocols prevent in-person visits.

The Site Investigators will complete the following, based on the information documented in the corresponding patient medical charts, and per Subject interaction and per clinical judgment guided by observing study Subject via in-person or remote/virtual visit:

- IGA of AK status (in relation to baseline), and current severity of skin photodamage in the AK treated area on the face or scalp (using EPQ item).
- Investigator rating of overall appearance of the AK treated area (using EPQ item).
- Modifications to tirbanibulin treatment characteristics following the initial prescription, if applicable.
- Perceptions and satisfaction with different attributes of tirbanibulin, and future preference to re-treat with tirbanibulin (using ad hoc and EPQ items).
- Any unplanned patient encounters in the past 8 weeks.
- Newly documented changes to patient clinical characteristics (incl. comorbidities and concomitant medications), as documented in medical charts in past 8 weeks since the baseline encounter.

- AEs, ADRs and LSRs observed in the past 8 weeks, as documented in the medical charts.
- Information on withdrawal from study (if occurred within the past 8 weeks).

The study Subjects will provide the following information via online survey portal or a mobile app:

- Perceptions of AK-related symptoms and impact of AK on Subject QoL, incl. emotional well-being and functioning, using Skindex-16.
- Self-rating of overall appearance of the AK treated area (using EPQ item).
- Perceptions and satisfaction with different attributes of tirbanibulin (using TSQM-9 and EPQ items, where applicable), and future preference to re-treat with tirbanibulin.

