2.2 Key Study End Points

The primary endpoint of the study will be the PROs, in terms of self-perceived AK symptoms and impact of AK on emotional well-being and functioning as measured using Skindex-16, at Week 8.

The secondary endpoint will be the proportion of Subjects with IGA success, defined as an IGA score of completely cleared (0) or partially cleared (1) in AK status in the treated area at Week 8.

Additional endpoints of the study will include (not exclusively):

- At Week 8, Mean satisfaction scores on TSQM-9 (effectiveness, convenience and overall satisfaction) as well as ad hoc satisfaction questions.
- At Week 8, Mean satisfaction scores on ad hoc physician satisfaction questionnaire.
- At Week 8, proportion of Subjects and Investigators rating the overall appearance of the AK treated area as ‘somewhat improved or much improved.’
- At Week 8, proportion of Subjects and Investigators reporting ‘somewhat likely or very likely’ to consider tirbanibulin in the future to retreat their AK.
- Frequency of documented adverse events (AEs), serious adverse events (SAEs) and LSRs during the first 8-weeks of the study observation period.
- Investigator rating of severity of skin photodamage at Weeks 8 and 24.
- Among Subjects with prior topical treatment experience at baseline:
 - At Week 8, proportion of Subjects and Investigators respectively rating ‘convenience/ease of use’ of tirbanibulin, and/or ‘overall satisfaction’ with tirbanibulin as ‘somewhat better or much better’ in comparison to previous topical treatments to treat their AK.
 - At Week 8, proportion of Subjects and Investigators respectively rating ‘duration of skin reactions’, ‘severity of skin reactions’ and/or ‘impact on daily activities due to skin reactions’ related to tirbanibulin, as ‘somewhat better or much better’ in comparison to previous topical treatments to treat their AK.

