6.2 Analysis Populations and Datasets

Statistical analysis and data tabulation will be performed using the following analysis populations unless specified otherwise:

- Safety Population: All patients who received at least one dose of tirbanibulin during the study observation period of 8-weeks related to primary endpoint, as part of usual care.
- Full Analysis Set (FAS): All patients within the Safety Population that had at least some data pertaining to the key variables studied at relevant timepoints, post-baseline.

All safety evaluations (part of additional objectives) will be conducted among the safety population, while FAS will be used to conduct analyses addressing rest of the study objectives, including the primary objective.

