6.5 Secondary Endpoint Analysis

The secondary endpoint of the study is the proportion of Subjects with an IGA success, defined as achieving a rating of ‘completely cleared’ (0) or ‘partially cleared’ (1) in IGA of AK status at Week 8. This analyses of IGA will be conducted using the FAS dataset.

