7.2 Tables from Clinician's DCF (FAS Population)

Clinician data is analyzed using the FAS dataset. In relevant instances (such as IGA and physician satisfaction evaluations), only FAS dataset with corresponding week clinician data is used. All data tables in this section correspond to FAS population.

Table 2.1 Site Characteristics

Domain	(N=x)
SC1: Current workplace	
Private, office-based practice	n (%)
Hospital-based practice	n (%)
SC2: Total number of board-certified dermatologists in the practice (including yourself, if applicable)	N, Mean (SD), Median, Min, Max
SC3: At present, how many patients with AKs do you personally manage in a given month?	N, Mean (SD), Median, Min, Max
SC4: How long have you been practicing dermatology, post-residency?	N, Mean (SD), Median, Min, Max

Note: Data from Clinician DCF. The denominator for the percentage is N which refers to total number of unique sites in PROSES study.

Table 2.2 Study Subject Selection Criteria

Domain (N=X)	Yes	No
SS1r1 Diagnosed with actinic keratosis of the face and/or scalp?	n (%)	n (%)
SS1r2 Has clinically typical, visible, and discrete AK lesions?	n (%)	n (%)
SS1r3 Considered a candidate for tirbanibulin (Klisyri®) AND you plan to administer tirbanibulin (Klisyri®) treatment?	n (%)	n (%)
SS1r4 At least 18 years of age at the time of initiation of tirbanibulin (Klisyri®) treatment?	n (%)	n (%)
SS1r5 Willing to avoid excessive sun or UV exposure, and/or use relevant sunscreen protection and protective clothing during the study duration.	n (%)	n (%)
SS1r6 Able to read and write English.	n (%)	n (%)
SS1r7 Able to provide consent to participate AND is willing to comply with study procedure?	n (%)	n (%)
SS2r1 Have another dermatological condition of the face that could interfere with the actinic keratosis clinical evaluations?	n (%)	n (%)
SS2r2 Hypertrophic AK lesions, open wounds or suspected skin cancers within close proximity of the treatment area	n (%)	n (%)
SS2r3 Anticipated need for in-patient hospitalization or in-patient surgery within the next 2 months.	n (%)	n (%)
SS2r4 Have a medical chart accessible to complete baseline data collection?	n (%)	n (%)

Note: Data from Clinician DCF. The denominator for the percentage is the number of patients with available data (N=X). There are no missing data.

Table 2.3 Patient Clinical Characteristics from Medical Chart

Character	Statistics	Baseline (N=XX)
PC1 Gender		
Male	n (%)	
Female	n (%)	
Other	n (%)	
PC2 Primary Health Insurance		

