How do you rate the current severity of skin photodamage in the AK affected area?			
Responses will need to be recoded	AK4	AK8_3	AK8_3
0. Absent	n (%)	n (%)	n (%)
1. Mild	n (%)	n (%)	n (%)
2. Moderate	n (%)	n (%)	n (%)
3. Severe	n (%)	n (%)	n (%)
Absent/ Mild (0/1)	n (%)	n (%)	n (%)
Moderate/Severe (2/3)	n (%)	n (%)	n (%)
Who did the evaluation of patient's AK severity?			
1. Dermatologist	AK5	AK8_4	AK8_4
2. Nurse practitioner	n (%)	n (%)	n (%)
3. Physician's assistant	n (%)	n (%)	n (%)
How was the evaluation of AK severity done?			
1. During in-person patient visit (face-to-face)	AK6	AK8_5	AK8_5
2. Via tele-health visit (video)	n (%)	n (%)	n (%)

Table 2.8 CFB for Current Severity of Photodamage in the Original Treated Area

Domain	CFB in Proportion at Week 8 N=X (%)	p-value	CFB in Proportion at Week 24 N=X (%)	p-value
How do you rate the current severity of skin photodamage in the AK affected area?				
Absent (0)	%		%	
Mild / Moderate / Severe (1 / 2 / 3)	%	p	%	p
Absent / Mild (0 / 1)	%		%	
Moderate / Severe (2 / 3)	%	p	%	p

Table 2.9 Subgroup Analysis of Current Severity of Photodamage in the Original Treated Area

Subgroups	% Absent / Mild (0 / 1)		Baseline		Week 8		Week 24	
		n (%)		n (%)	P	n (%)	P	
Gender								
Male								
Female								
Age Group								
≤ 49 years								
50 – 64 Years								
≥ 65 years								
AK Treatment Location								
Face								
Scalp								
Both								
Fitzpatrick Skin Type								
I / II								
III / IV / V / VI								
Skin Photodamage								
Absent/mild								
Moderate/Severe								
History of Skin Cancer								
Yes								
No								
Prior Treatment Experience: Use of Cryosurgery								
Yes								
No								
Prior Treatment Experience: Use of Other Topical Treatments								
Yes								
No								
Prior Treatment Experience: Treatment Naïve at Baseline								
Yes								
No								

P-values correspond to CFB at respective time periods, within the corresponding strata.

Table 2.10 Clinician Evaluation of IGA in the Original Treated Area

Character	Week 8 (N=x)	Week 24 (N=X)
Overall, how is your patient's AK in the original treated area right now?		
Responses will need to be recoded	AK8_1	AK8_1
0. Completely Cleared	n (%)	n (%)
1. Partially Cleared	n (%)	n (%)
2. Moderately Cleared	n (%)	n (%)
3. Minimally Cleared	n (%)	n (%)
4. Not Cleared	n (%)	n (%)
(0 / 1) Completely/Partially Cleared	n (%)	n (%)
2 Moderately Cleared	n (%)	n (%)

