3 /4 Minimally/ Not Cleared	n (%)	n (%)

Table 2.11 IGA Success at Week 8 in the Original Treated Area

Character	Week 8
IGA Success	N=x
No	n (%)
Yes	n (%)

Note: IGA success at Week 8, defined as an IGA score of completely cleared (0) or partially cleared (1) in AK status in the original treated area at Week 8. The denominator for the percentages is the number of patients with available data (N=XX). X patients had missing data at Week 8.

Table 2.12 Subgroup Analysis of IGA Success

% IGA Success (Completely/Partially Cleared)		Week 8 n (%)	Week 24 n (%)
Subgroups			
Gender			
Male			
Female			
p -value			
Age Group			
≤ 49 years			
50 – 64 Years			
≥ 65 years			
p -value			
AK Treatment Location			
Face			
Scalp			
Both			
p -value			
Fitzpatrick Skin Type			
I / II			
III / IV / V / VI			
p -value			
Skin Photodamage			
Absent/mild			
Moderate/Severe			
p -value			
History of Skin Cancer			
Yes			
No			
p -value			
Prior Treatment Experience: Use of Cryosurgery			
Yes			
No			
p -value			
Prior Treatment Experience: Use of Other Topical Treatments			
Yes			
No			
p -value			

Prior Treatment Experience: Treatment Naïve at Baseline

Yes

No

p-value

P-values correspond to difference between strata within respective time periods.

Table 2.13 Clinician Evaluation of Overall Appearance in the Original Treated Area

Character	Week 8 (N=x)	Week 24 (N=X)
Compared to 8 / 24 weeks ago, how has the patient's overall appearance of the skin in the original AK treated area changed?		
1. Much Worse	AK8_2	AK8_2
2. Somewhat Worse	n (%)	n (%)
3. No Change	n (%)	n (%)
4. Somewhat improved	n (%)	n (%)
5. Much Improved	n (%)	n (%)
(1/2) Much/Somewhat Worse	n (%)	n (%)
(3) No Change	n (%)	n (%)
(4/5) Somewhat/Much Improved	n (%)	n (%)

Table 2.14 Subgroup Analysis of Clinician Evaluation of Overall Appearance in the Original Treated Area

% Somewhat / Much Improved	Week 8 n (%)	Week 24 n (%)
Subgroups		
Gender		
Male		
Female		
p -value		
Age Group		
≤ 49 years		
50 – 64 Years		
≥ 65 years		
p -value		
AK Treatment Location		
Face		
Scalp		
Both		
p -value		
Fitzpatrick Skin Type		
I / II		
III / IV / V / VI		
p -value		
Skin Photodamage		
Absent/mild		
Moderate/Severe		
p -value		
History of Skin Cancer		
Yes		
No		
p -value		
Prior Treatment Experience: Use of Cryosurgery		
Yes		
No		
p -value		
Prior Treatment Experience: Use of Other Topical Treatments		
Yes		
No		

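### SAP 7 makes the FAS depend on the Week-8 patient survey, contradicting SAP 6.2 and needlessly narrowing the clinician IGA denominator; SAP 6.9 also cuts back Protocol 12.8

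*SAP*

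**What the plan says.** The FAS is defined twice. SAP 6.2, in the same words as Protocol 12.2, takes "All patients within the Safety Population that had at least some data pertaining to the key variables studied at relevant timepoints, post-baseline". The opening of SAP 7 instead requires at least one dose plus some primary-endpoint PRO data at Week 8, and puts this into practice as: "patients who completed the study survey at Week 8 will be included in FAS".

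The endpoint concerned is not patient-reported. Under the heading of key endpoints, SAP 2.2 states: "The secondary endpoint will be the proportion of Subjects with IGA success". The rating is made by the Site Investigator (SAP 5.3.1). SAP 6.5 adds: "This analyses of IGA will be conducted using the FAS dataset". SAP 7.2 says that for IGA and similar clinician evaluations "only FAS dataset with corresponding week clinician data is used", and that every table in that section is an FAS table. Tables 2.10 and 2.12 have Week-8 and Week-24 columns; Table 2.11 is Week 8 only.

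On missing data, Protocol 12.8 says without condition that the effect of missing data, its reasons, time to drop-out, and key outcomes in completers versus discontinuers will be explored. SAP 6.9 keeps the first item only if the amount of missing data is unusual, sets no threshold, and does not mention the rest.

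**The concern.** A clinician's rating of lesion clearance does not need a patient questionnaire to be valid. Under SAP 7, though, the questionnaire decides whether the rating counts. Valid data on the study's stated effectiveness measure would be set aside by a rule that the SAP's own populations section and the protocol do not contain. The rule also reaches forward: a missed Week-8 survey removes a patient's Week-24 IGA as well.

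The missing-data point is related. SAP 6.3.1 assumes that all missing data are uninformative, and SAP 6.7 plans no imputation. The comparison of completers with discontinuers in Protocol 12.8 is the planned look at whether that assumption is reasonable, and the SAP has no place for it.

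**Working it through.** **1. No plan figure to reproduce.** SAP 6.1 reports no sample size calculation. Neither document gives an expected IGA rate, a survey completion rate or an FAS size. The only count is 300 dosed patients (SAP 7).

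**2. Trace one patient.** Take a dosed patient with clinician IGAs at Weeks 8 and 24 and no Week-8 survey.

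| Rule | Result |
|---|---|
| SAP 6.2 / Protocol 12.2 | In the FAS, if IGA is a key variable. The term is undefined, but SAP 2.2 lists IGA success among the key endpoints |
| SAP 7 | Not in the FAS |
| SAP 6.5 with SAP 7.2, using the SAP 7 set | Absent from Tables 2.10, 2.11 and 2.12, including the Week-24 columns of 2.10 and 2.12 |

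**3. Can such a patient exist?** Protocol 7.3 has the investigator complete the assessment from chart, contact and observation. For patients it says: "The study Subjects will provide the following information via online survey portal or a mobile app". Protocol 11 describes two linked but distinct data sources, and SAP Table 4.11 counts patient and clinician surveys in separate columns. So the case is possible; the documents do not say how often it occurs.

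**4. Would the planned output show it?** The missing-data note to Table 2.11 works within the FAS, so it counts survey completers without an IGA, not the reverse. Table 4.11 does not cross-classify the two surveys. No Safety-population table in SAP 7.4 reports IGA. The listings in Appendix D would allow reconstruction, but they are not a summary.

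**5. Scale, by assumption only.** Suppose the survey-based FAS has 270 patients and 189 successes: 189/270 = 70.0%. The Wald 95% half-width is 1.96 × √(0.70 × 0.30 / 270) = 0.0547, about 5.5 points. Add k patients with an IGA but no survey, with success rate q:

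shift = k/(270 + k) × (q − 0.70)

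| k | Weight k/(270+k) | None succeed | All succeed |
|---|---|---|---|
| 0 | 0 | 70.0% | 70.0% |
| 5 | 1.8% | 189/275 = 68.7% | 194/275 = 70.5% |
| 10 | 3.6% | 189/280 = 67.5% | 199/280 = 71.1% |
| 15 | 5.3% | 189/285 = 66.3% | 204/285 = 71.6% |
| 30 | 10.0% | 189/300 = 63.0% | 219/300 = 73.0% |

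The ceiling from this base is k = 30 (300 − 270), meaning every non-completer has an IGA. Only its lower extreme, −7.0 points, exceeds the half-width. With q = 50%, the shift at k = 30 is 0.10 × (0.50 − 0.70) = −2.0 points; with q = 70% it is zero at any k.

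**6. Missing-data items side by side.**

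| Item | Protocol 12.8 | SAP |
|---|---|---|
| Effect of missing data on robustness | Unconditional | Conditional, no threshold (6.9) |
| Reasons | Explored | Discontinuation reasons by visit (Tables 4.11–4.12) |
| Time to drop-out | Explored | By visit only (Tables 4.11–4.12) |
| Completers versus discontinuers | Explored | Absent from 6.9 and 7.5 |

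SAP 7.5 holds one table, IGA success by visit type. SAP 6.8 expects missed and rescheduled visits, which makes it harder still to say what amount would be unusual.

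**The case against.** SAP 7 can be read as the concrete form of a loose definition. SAP 6.2 leaves its key variables and timepoints undefined, Protocol 12 leaves detail to the SAP, and SAP 7 directly heads the table shells. One common cohort also suits the patient–clinician comparisons in SAP 7.3. This reading fits Skindex-16. It does not fit a clinician-rated endpoint or Week-24 data, so it softens the contradiction without removing it.

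The number affected may well be small: subjects are paid for completing surveys and may be sent reminders (Protocol 6.3.2), and sites try to contact those who do not complete (Protocol 7.6). That stands.

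The SAP 7 set also serves a purpose. If the wider FAS were applied to every table, patients with baseline data only could enter the baseline columns of Skindex Tables 1.6 to 1.8, mixing attrition with change. That stands too, and it shapes the fix.

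On missing data, patients who leave before Week 8 have few outcomes to compare, and with two post-baseline encounters the by-visit tables already give most of the timing. This limits what the comparison can show; it does not license omitting one that the protocol says will be done.

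A reader might want best-case and worst-case bounds for missing IGAs. They are not needed to resolve either inconsistency, and they would run against the no-imputation rule in Protocol 12.7 and SAP 6.7.

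**Conclusion.** The contradiction is in the text, and its consequence for Tables 2.10 to 2.12 follows from SAP 6.5, 7 and 7.2 read together. It leaves the only secondary endpoint with an inconsistent and needlessly restrictive denominator.

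A reader might infer that the reported IGA success rate will be inflated because non-responders did worse. The documents do not support that. They give neither the number of patients with an IGA but no survey nor any outcome in them; the shift could go either way and may be nil. The 270, the 70% and every k above are assumptions.

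A reader might also infer that the SAP discards all information on drop-out. It does not: Tables 4.11 and 4.12 give discontinuation reasons and timing by visit. What is lost is the unconditional commitment to examine missing data and the outcome comparison between completers and discontinuers.

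Both points should be fixed, because the choice of denominator should be settled before results are seen and the repair is cheap.

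**What to change.** **(a) Populations.** Keep the SAP 6.2 / Protocol 12.2 wording as the single FAS definition; a clause naming the key variables, IGA among them, would help. Rename the Week-8-survey set in SAP 7 as a PRO-evaluable set, used for the Skindex-16 and other Week-8 patient-reported tables, with change from baseline computed in patients who have both values. Analyse IGA success at each visit in all dosed patients with a clinician IGA at that visit, whether or not they answered the survey. SAP 6.5 can then stand, and the SAP 7.2 rule gives that denominator. Add a line to Tables 2.10 and 2.11 with the number of patients who have an IGA but no survey.

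**(b) Missing data.** Remove the condition in SAP 6.9. Add one descriptive table to SAP 7.5 comparing available key outcomes, mainly at Week 8, in study completers and in those who discontinued. Tables 4.11 and 4.12 can stay as they are.

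**Cost.** SAP wording, one count line and one table shell, all from data the plan already collects.
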